### **7.2. Study Treatments**

[REDACTED]  
[REDACTED]  
[REDACTED] Duration of exposure will be summarized descriptively using number, mean, standard deviation, median, minimum and maximum at [REDACTED], by dose group and overall. Counts and percentages will be provided for subjects exposed for [REDACTED]

Study treatment compliance rate will be calculated as the ratio of the total number of tablets taken to the total number of tablets assigned, where the total number of tablets taken is ( [REDACTED] ). [REDACTED]

[REDACTED]

[REDACTED]

[REDACTED]

[REDACTED]

[REDACTED]

[REDACTED]. A subject listing of study treatment compliance will be provided.

## **8. Efficacy Analysis**

This is a pharmacodynamic study. Analysis of the primary pharmacodynamic endpoint, the Modified Ashworth Score, is described in Section 8.1. Analyses for the secondary endpoints, spasm frequency, nighttime awakening due to spasms, CGIC and SGIS are described in Sections 8.2. The primary and secondary efficacy analyses will be based on the ITT population.

### **8.1. Primary Efficacy Analysis**

[REDACTED]

[REDACTED] the duration of effect, p-values will be used as a guide; a hierarchical approach to the analysis of time points will be used as described below. For these reasons, the p-values will not be adjusted for the multiple comparisons performed.

The baseline total Modified Ashworth Score is defined as the total score at [REDACTED]. Statistical significance of [REDACTED]

[REDACTED] total Modified Ashworth Score will be assessed. At each time point, the change from baseline will be computed. A hierarchical testing procedure will be used to assess duration of effect separately for each dose level. [REDACTED]

[REDACTED]

[REDACTED] total Modified Ashworth Score as a covariate, and the interaction between treatment group and baseline Modified Ashworth Score. [REDACTED]

[REDACTED]

[REDACTED]  
[REDACTED].  
This procedure will be continued until reaching a time point at which the difference between active and placebo is statistically significant.

[REDACTED]  
[REDACTED]  
[REDACTED], the corresponding standard error (SE), 95% Confidence Interval (CI), and the p-value representing the significance of treatment effect will be displayed for each timepoint in a separate table. The observed score and change from baseline will be displayed in separate boxplots by time points.

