#### **4. General Statistical Considerations**

In general, continuous variables will be summarized with descriptive statistics (number of observations, mean, standard deviation, median, minimum, maximum, and 95% CI) and categorical variables will be summarized with count and percentage, unless otherwise specified. If there is only one observation, the standard deviation will be displayed as NE (Not Estimable). The p-values will be two-sided and rounded to four decimal places, and a significance level of alpha ( $\alpha$ ) = 0.05 will be used to reject the null hypothesis. Baseline will be defined as the last pre-dose non-missing measurement, unless specified otherwise.

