##### **4.1. Sample Size**

[REDACTED]

[REDACTED] 31 evaluable subjects in each treatment group is required to provide 90% power, assuming a common standard deviation [REDACTED]. To account for the drop-out rate of 30%, approximately 135 subjects will be randomized in this trial.

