##### **4.2. Randomization, Stratification, and Blinding**

Eligible subjects will be randomized to receive [REDACTED]

[REDACTED].

[REDACTED]

[REDACTED]

[REDACTED] as required for regulatory reporting

purposes. [REDACTED]  
[REDACTED]

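### Does the treatment-by-baseline interaction in the primary model turn the treatment p-value into a low-powered test at an Ashworth score of zero?

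*Combined protocol and SAP*

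**What the plan says.** SAP section 8.1 (Primary Efficacy Analysis) analyses change from baseline in total Modified Ashworth Score at each time point, in a hierarchy run separately for each dose level. The visible part of the model statement has baseline "total Modified Ashworth Score as a covariate, and the interaction between treatment group and baseline Modified Ashworth Score". Text is redacted directly before and after this clause.

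The procedure turns on whether active and placebo differ significantly at a time point. For the output, the name of the estimate is redacted, and then "the corresponding standard error (SE), 95% Confidence Interval (CI), and the p-value representing the significance of treatment effect will be displayed for each timepoint". The same section describes the p-values as a guide to duration of effect.

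The SAP's abbreviation list defines LS as least square, but the term appears nowhere in the visible text.

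Section 4.1 sizes the trial on a difference between groups: "31 evaluable subjects in each treatment group is required to provide 90% power, assuming a common standard deviation". The difference and the SD are redacted. Section 4 sets two-sided tests at 0.05.

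**The concern.** Once treatment interacts with a continuous covariate, there is no single treatment effect: the active-placebo difference depends on the baseline score. If the covariate enters uncentred, the treatment coefficient in the model output is the difference at a baseline score of zero, that is, no measured spasticity. The trial enrols people with spasticity due to MS, so zero is probably an extrapolation, and the coefficient is estimated less precisely than the difference at the mean.

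The visible text gives one treatment p-value per time point and does not say at which baseline value it is taken. If it came from the raw coefficient, the time-point hierarchy would rest on an underpowered test of the wrong quantity. The p-value could also contradict the estimate and interval printed beside it.

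**Working it through.** **Inputs.** Two-sided alpha 0.05 (section 4); 31 evaluable subjects per group, 90% power, 30% drop-out and about 135 randomized (section 4.1). Three inputs are assumptions because the documents do not show them: the standardised effect (back-solved below), the number of groups, and r = baseline mean / baseline SD (range 0.5 to 3).

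**Step 1: the plan's own figure.** 31 / (1 − 0.30) = 44.3, rounded up to 45 per group. Three groups give 3 × 45 = 135, which matches section 4.1. Two groups give 90 and four give 180, so three equal groups are assumed.

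**Step 2: implied effect.** d = (1.960 + 1.282) × √(2/31) = 0.823 by the normal approximation, or 0.837 by the t-test. The 90% itself cannot be checked independently, because the effect and SD are redacted.

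**Step 3: precision at a chosen baseline value.** With separate slopes per group, the variance of the active-placebo difference at baseline value x is approximately

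(2σ²/n) × [1 + (x − mean)²/SD²].

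At x = mean the bracket is 1. At x = 0 it is 1 + r², so the standard error is multiplied by √(1 + r²).

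**Step 4: power under each reading, equal true slopes.** At x = 0, power is approximately Φ(3.242/√(1 + r²) − 1.960). For r = 2: 3.242/2.236 = 1.450, and 1.450 − 1.960 = −0.510, which gives 0.305. The simulations use three groups of 31 with the interaction fitted.

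| r | SE multiplier | Power at zero (formula) | Power at zero (simulated) | Power at mean (simulated) |
|---|---|---|---|---|
| 0.5 | 1.12 | 0.83 | 0.81 | 0.90 |
| 1 | 1.41 | 0.63 | 0.61 | 0.89 |
| 2 | 2.24 | 0.31 | 0.29 | 0.89 |
| 3 | 3.16 | 0.18 | 0.18 | 0.90 |

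Power at zero falls below half of 90% only from about r = 1.5 (0.44).

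**Step 5: unequal slopes** (two-group simulation). If the effect is proportional to baseline, power at zero is about 0.05. If the effect at zero is twice that at the mean, power at zero is 0.99 at r = 1, 0.79 at r = 2 and 0.50 at r = 3. The contrast at the mean keeps 0.87 to 0.90 throughout.

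The loss therefore comes from the evaluation point, not from the interaction term. The remaining question is which evaluation point the SAP uses.

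**Step 6: what the text supports.** Three visible features describe a pairwise group contrast:

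- The hierarchy is run for each dose against placebo and asks about a difference between the two.
- The output is a named estimate, with the name redacted, accompanied by its own SE, its 95% CI and a p-value.
- LS is defined as an abbreviation but unused in the visible text, so it probably stands in a redacted part.

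An LS-mean difference is normally evaluated at the mean of the covariate, and this needs no explicit centring. No visible text points to the raw coefficient at zero.

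**The case for a change.** The strongest case for the concern is that the visible wording leaves the point open and the consequence could be large. The SE is tied to the redacted estimate, while the p-value is described separately: "the p-value representing the significance of treatment effect will be displayed for each timepoint in a separate table". A programmer could print the LS-mean difference and interval beside the p-value of the uncentred treatment term. In a three-group simulation with equal slopes, the two tests reached opposite conclusions in 31% of trials at r = 1, 62% at r = 2 and 74% at r = 3. Calling the p-values a guide softens this only in part, because the hierarchy still turns on significance. Stating the evaluation point would cost one sentence.

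The mechanism and these figures stand. What does not stand is the step from a possible programming choice to a defect in the plan. The argument needs the redacted estimate to be an LS-mean difference and the p-value beside it to belong to a different quantity, and nothing visible supports that combination. Redacted text cannot be counted as absent, and the gaps fall where the evaluation point would be written.

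The other proposal, to drop the interaction from the primary model, brings no power: the average-effect test has about 90% with or without it, provided the contrast is taken at the mean. Allowing unequal slopes is a legitimate modelling choice.

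**Conclusion.** The concern does not hold. The interaction is in the primary model, and an uncentred test at zero would indeed be weak: about 63%, 31% and 18% power at r = 1, 2 and 3 with equal slopes. The SAP does not say that it uses that test. Its visible wording fits an LS-mean contrast for each dose against placebo which, taken at the mean baseline, keeps about 89 to 90% power with equal slopes and 87 to 90% with the unequal slopes tried.

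This rests on three equal groups, a back-solved effect of 0.82 to 0.84 SD, and the usual practice of evaluating LS means at the covariate mean. The visible text does not prove that last point, but it gives no ground for the opposite reading. A claim that most of the power is lost would also need r above about 1.5 and an effect that is not larger at low baseline; the documents give neither. Writing out the evaluation point would only confirm what standard LS-mean practice already supplies.

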## 8.2. Secondary Efficacy Analyses

[REDACTED]. For the spasm frequency and nighttime awakening score, baseline is the measurement taken at the screening visit.

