## **7. Treatments and Medications**

### **7.1. Prior and Concomitant Medications**

A medication will be categorized as prior medication if the medication end date is before the first dose date. A medication will be categorized as a concomitant medication if the medication end date is after the first dose date or is ongoing at study completion. If the start or end date of a medications is missing, it will be imputed as described in Appendix 11.4. All prior and concomitant medications will be coded to Anatomical Therapeutic Chemical (ATC) Class 3 and Preferred Name according to the latest version of the World Health Organization Drug Dictionary (WHODD).

The number and percentage of subjects in the Safety population taking prior or concomitant medications will be summarized by ATC class and Preferred Name in two separate tables, by dose group and overall. In addition, the prior medications for MS and spasticity, and the medications subjects washed out from in order to enter the study, as well as neurological and anti-spasticity concomitant medications, and concomitant medications present at Day 23 check-in will be summarized separately. Antispasticity and neurological medications will be identified via a Medial Monitor review of coded terms prior to database lock. Subject listings of prior and concomitant medications will be provided. The medications taken within 30 days prior to the screening visit will be listed in a separate listing.

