### 8.2.1. Spasm Frequency

The [REDACTED] baseline spasm [REDACTED] will be summarized by visit. Statistical significance of treatment difference [REDACTED]

[REDACTED] [REDACTED]  
[REDACTED]  
[REDACTED]

[REDACTED].  
[REDACTED]

[REDACTED], 95% CI, and the p-value representing the significance of treatment effect will be displayed in a table. The change from baseline in spasm frequency will be displayed in histograms for each treatment group by visit. The actual score will be listed in a data listing.

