#### **8.2.2. Night Time Awakening Score**

The nighttime awakening score will be summarized in the same way as spasm frequency.

[REDACTED]  
[REDACTED]  
[REDACTED]. The observed scores will be listed in a data listing. The change from baseline in nighttime awakening score will be displayed in histograms for each treatment group by visit.

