## 11.5. Schedule of Study Procedures

Subject will check-out of the clinic following the [REDACTED] .

Subjects will be required to be currently receiving prior to enrollment, and

Hematology: red blood cell (RBC) count, hemoglobin, total white blood cell (WBC) count, differential WBC count, platelet count; serum chemistry: sodium, potassium, chloride, blood urea nitrogen (BUN), creatinine.

4 Within 2 hours

23 or 24 hours post-dose

Within 10 minutes of 12-lead ECG

Dosing at time “0”

Within 2 hours pre-dose

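### Should spasm frequency and nighttime awakening keep the screening visit as baseline when subjects were washed out of medication to enter?

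*Combined protocol and SAP*

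**What the plan says.** Section 4 of the SAP gives the default: "Baseline will be defined as the last pre-dose non-missing measurement, unless specified otherwise". Section 8.2 uses the room this leaves: "For the spasm frequency and nighttime awakening score, baseline is the measurement taken at the screening visit". The text just before that sentence is redacted.

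Section 7.1 plans a separate summary of "the medications subjects washed out from in order to enter the study". It does not show which drugs these were, how many subjects stopped them, for how long, or when relative to the screening visit.

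The screening baseline feeds the displays in Section 8.2.1: "The change from baseline in spasm frequency will be displayed in histograms for each treatment group by visit". Section 8.2.2 carries this over: "The nighttime awakening score will be summarized in the same way as spasm frequency". Section 8.2.1 also plans a test of the treatment difference, with a confidence interval. The model is redacted.

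**The concern.** A washout done to qualify for a study usually comes after a first screening contact and before dosing. If that was the order here, the screening score describes the subject on earlier therapy, while study drug starts from a different state. Each arm's change from baseline would then be washout worsening plus response, and an effective arm could look unchanged or worse in the histograms. A score further from the treatment period may also predict the post-dose score less well, which widens the interval for the treatment difference. The plan's default rule would seem to avoid both problems, and no reason for leaving it is visible.

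**Working it through.** **Inputs.** Baseline rules: Sections 4 and 8.2. Washout: Section 7.1. Test level: Section 4, which says "The p-values will be two-sided and rounded to four decimal places" and that an alpha of "0.05 will be used to reject the null hypothesis". Section 4.1: 31 evaluable subjects per group, 90% power, 30% drop-out, about 135 randomised. Neither score has a standard deviation or a correlation in the documents, so those below are assumptions.

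**1. The plan's own figure.** The number of groups is redacted. With three assumed, 31 × 3 = 93 and 93/0.70 = 133. Rounding up within group, 31/0.70 gives 45, and 45 × 3 = 135. Two groups give 89 to 90 and four give 178 to 180, so three fits. This figure belongs to the primary endpoint and does not depend on Section 8.2.

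**2. When does the exception alter the baseline?**

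| Screening score relative to washout | Later pre-dose score collected? | Effect of deleting the exception |
|---|---|---|
| Before | No | None: Sections 4 and 8.2 select the same value |
| After | No | None, and no washout shift |
| After | Yes | A different value, but no washout shift |
| Before | Yes | Removes the washout shift from within-arm change; precision may improve |

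Only the last row supports the concern, and it also needs the washed-out drugs to affect these two scores. The design text in Section 3.1 is redacted. Section 11.5 survives only as footnotes, and the one on medication before enrolment is a fragment: "Subjects will be required to be currently receiving prior to enrollment, and". It does not settle the order.

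**3. Between-arm difference.** Let S be the screening score and Y the post-dose score. Randomisation gives S the same expectation in every arm, so E(Y − S | active) − E(Y − S | placebo) = E(Y | active) − E(Y | placebo). A washout shift common to the arms cancels.

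**4. Precision.** With correlation r between baseline and post-dose score and equal variances, the variance is 2σ²(1 − r) for a change score and σ²(1 − r²) after baseline adjustment. For r = 0.6 against 0.4:

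- change score: 0.8 against 1.2, ratio 1.5, standard error × 1.22
- adjusted: 0.64 against 0.84, ratio 1.31, standard error × 1.15

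To express this as power, take 31 per group and an effect giving 90% with the post-washout baseline. That effect is √(2/31) × (1.960 + 1.282) = 0.823 residual standard deviations. For a standard-error ratio k, power is Φ(3.242/k − 1.960).

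| r post-washout / screening | Change score: SE ratio, power | Adjusted: SE ratio, power |
|---|---|---|
| 0.6 / 0.5 | 1.12, 83% | 1.08, 85% |
| 0.6 / 0.4 | 1.22, 75% | 1.15, 81% |
| 0.7 / 0.5 | 1.29, 71% | 1.21, 76% |
| 0.7 / 0.3 | 1.53, 56% | 1.34, 68% |
| equal | 1.00, 90% | 1.00, 90% |

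**5. A worked illustration.** Assume half the subjects wash out with a shift of +1 SD, each score carries 0.7 of the one before it with residual variance 0.51, and the true effect is −0.50 SD.

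- Placebo mean change: 0.7 × 0.5 = +0.35 SD from screening, and 0.35 − 0.50 = −0.15 SD from the post-washout score. The within-arm picture does move.
- Difference between arms: −0.50 SD with either baseline (simulated −0.503 and −0.501).
- Simulated standard error: 0.270 from screening and 0.200 from the post-washout score, ratio 1.35.
- Source of that ratio: without the washout term, the change variances are 0.51² + 0.49 × 0.51 + 0.51 = 1.02 and 0.3² + 0.51 = 0.60, and √(1.02/0.60) = 1.30. Most of the loss thus comes from the assumed decay of correlation over time, and little from the washout.

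**The case for a change.** The strongest case for a change is that it costs one sentence. The exception is in unredacted text with no visible reason. A washout done to enter the study makes screening-first the likelier order. If a later pre-dose score exists, the default rule recovers a better baseline; if not, the default returns screening anyway.

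The mechanism stands, and so does the likely order. Three things weaken the rest:

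- The gain needs a second pre-dose measurement of these scores, and no visible text shows one.
- The default is not free of cost. A subject missing the later score would fall back to screening, so one baseline variable would mix values from before and after washout. A fixed visit treats all subjects alike.
- The advice for the case with no later score, to rely on the difference between arms, describes what Section 8.2.1 already tests. The histograms are drawn for each treatment group, so the placebo panel shows any common shift next to the active panels.

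**Conclusion.** No change is called for. The exception is one that Section 4 permits, and the randomised comparison is unbiased with either baseline. Replacing screening would help only if three facts hold that cannot be seen: the score was taken before washout, the stopped drugs influence it, and it was measured again before dosing. Even then the gain is efficiency and easier reading of within-arm change for two secondary endpoints. Over the assumed correlations, the standard error would be 8% to 34% larger with baseline adjustment and 12% to 53% larger for change scores, falling to zero if the correlations are equal. None of these figures can be tied to the redacted model. Analysts can handle the remaining point in the ordinary way, by reading each arm's change from screening against placebo and not as a drug effect in itself. The primary analysis and the planned 135 subjects are untouched.

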### 8.2.1. Spasm Frequency

The [REDACTED] baseline spasm [REDACTED] will be summarized by visit. Statistical significance of treatment difference [REDACTED]

[REDACTED] [REDACTED]  
[REDACTED]  
[REDACTED]

[REDACTED].  
[REDACTED]

[REDACTED], 95% CI, and the p-value representing the significance of treatment effect will be displayed in a table. The change from baseline in spasm frequency will be displayed in histograms for each treatment group by visit. The actual score will be listed in a data listing.

#### **8.2.2. Night Time Awakening Score**

The nighttime awakening score will be summarized in the same way as spasm frequency.

[REDACTED]  
[REDACTED]  
[REDACTED]. The observed scores will be listed in a data listing. The change from baseline in nighttime awakening score will be displayed in histograms for each treatment group by visit.

#### **8.2.3. CGIC**

The CGIC at [REDACTED]  
[REDACTED]  
[REDACTED]  
[REDACTED]  
[REDACTED].

#### **8.2.4. SGIS**

The SGIS will be summarized in the same way as the CGIC for the categorical outcomes

[REDACTED]  
[REDACTED]  
[REDACTED].

### **9. Safety Analysis**

Safety evaluations will be based on the incidence, severity, and causality of AEs, vital signs, Columbia-Suicide Severity Rating Scale C-SSRS, electrocardiogram (ECG), and clinical laboratory results. The safety analysis for female subjects will also include urine pregnancy results. All safety analyses will be conducted on the Safety population.

### **9.1. Adverse Events**

Treatment-emergent adverse events (TEAEs) will be used for summary and analysis purposes. A TEAE is defined as: any new event that occurred [REDACTED] [REDACTED] [REDACTED], a condition that existed before drug administration but increased in severity, or a condition that existed prior to drug treatment but increased in frequency of occurrence. A treatment-emergent serious adverse event (SAE) is defined as any treatment-emergent event that results in death, is immediately life threatening, requires inpatient hospitalization or prolongation of existing hospitalization, results in persistent or significant disability/incapacity, is a congenital anomaly/birth defect, or is an important medical event. TEAEs will be recorded [REDACTED]. [REDACTED] will be coded to System Organ Class (SOC) and Preferred Terms (PTs) using the latest version of of MedDRA®.

A treatment-related AE is an event that is considered possibly or probably related to study drug, in the judgment of the investigator. If the AE start date is missing, it will be imputed as described in Appendix 11.4.

The following summaries of AEs by SOC and PT will be provided:

- Overall TEAE summary, including:
  - Incidence of subjects with one or more TEAE
  - Incidence of TEAEs by highest relationship
  - Incidence of TEAEs by highest severity
  - Incidence of TEAEs by action taken
  - Incidence of TEAEs by outcome
  - Incidence of treatment-emergent SAEs

- TEAEs by SOC and PT
- TEAEs by descending order of frequency of PTs
- TEAEs by SOC and PT and highest relationship to treatment
- Treatment-related TEAEs by SOC and PT
- TEAEs by SOC and PT and highest severity
- Treatment-related TEAEs by SOC and PT and highest severity
- TEAEs by SOC and PT and sex
- TEAEs by SOC and PT and age group
- TEAEs by SOC and PT and race
- TEAEs by SOC and PT and frequently used concomitant medications (i.e., medications used by 20% or more of the subjects overall)
- TEAEs by SOC and PT and concomitant medications present on [REDACTED]
- TEAEs leading to treatment discontinuation by SOC and PT
- SAEs by SOC and PT
- Fatal SAEs by SOC and PT
- Treatment-related SAEs by SOC and PT

At each level of summarization, a subject will be counted only once for each AE he/she experiences within that level. For the summary by relationship, if a subject has more than one AE on different levels, the most related AE will be counted. For the summary by severity, if a subject has more than one AE on different levels, the most severe AE will be summarized in the table. All summaries by SOC/PT will be presented in the descending order of frequency in the total column (i.e., all treatment groups combined). Data listings will be provided for all AEs, SAEs, and AEs leading to study drug discontinuation.

